If volunteers complete the informed consent/assent process and are eligible for participation, they will be randomized to double blind varenicline or placebo and will proceed with treatment. In order to avoid accidental bias, we will utilize a stratified urn randomization procedure. We will stratify by the prognostic covariates age (14-17 versus 18-21) and baseline smoking level (<12 versus 12 or more cigarettes per day, based on median baseline smoking in our prior randomized adolescent smoking cessation trial). The age stratification will ensure that both younger and older adolescents will be equally represented in the varenicline and placebo groups. The smoking level stratification will help avoid significantly discrepant baseline smoking between treatment groups. We considered additional stratification variables (e.g., gender, severity of nicotine dependence, presence of other smokers in household, history of attention-deficit/hyperactivity disorder), but, amid concern over excessive division of participants among multiple cells, judged that these could be adequately explored as covariates during efficacy analyses (see Section C3f).

C3d. Treatment

Pharmacological Intervention

The MUSC Investigational Drug Service (IDS) will obtain varenicline 0.5 mg and 1 mg tablets and matched placebo tablets. All tablets will be packaged in blister packs, with individual labels for time/date of each dose (e.g., Tuesday morning October 5th). This date- and time-labeled blister pack method has demonstrated superior participant adherence, compared to traditional packaging, and offers the additional advantage of tracking the exact timing of any missed doses (53-55). The IDS successfully used identical methods for medication/placebo dispensing in our adolescent varenicline pilot study.

If assessment procedures reveal that a participant meets inclusion criteria, the IDS will randomize the participant to varenicline or placebo in double-blind fashion. He/she will be given a 7-day supply of medication to take home. Participants will be given an additional 7-day supply "replacement pack" of medication for use in the event that they cannot make it back for a visit within the 7-day window between visits.

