5. **Adverse Events:** During psychiatric and medical evaluation at each visit, adverse events will be documented and rated as mild, moderate, or severe. The study medical clinician will additionally assess relatedness of adverse events to study interventions (i.e., not at all, unlikely, uncertain, possible, probable, definite). The Data and Safety Monitoring Board (See Human Subjects Section 4) will evaluate adverse event information (e.g., frequency, severity, number leading to discontinuation) by treatment group during closed sessions of yearly meetings. Established procedures will be used in the event of a serious adverse event (SAE; see Human Subjects Section 4.6).
6. **Review of Systems:** A detailed, structured psychiatric and medical review of systems (41) will be conducted during weekly medication monitoring visits to augment open-ended adverse event questioning. We have utilized this method with success in prior adolescent smoking cessation pharmacotherapy studies. This exhaustive, systematic method reduces the likelihood of underreported adverse events.
7. **Penetration of Blind Assessment:** At key time-points during the study, participants will be asked by a study clinician if they think they are receiving active study medication or placebo. The study clinician will also document whether they think the participant is receiving active medication or placebo.

Self-Report Craving, Withdrawal, and Satisfaction Forms

1. **Questionnaire on Smoking Urges—Brief (QSU-B)** (76): Participants will complete this brief form detailing symptoms of nicotine craving. Participants will additionally complete ratings of current level of craving and maximum & average levels of craving over the last week. Similar measures of current, maximum, and average ratings of ability to resist temptation to smoke will be collected.
2. **Minnesota Nicotine Withdrawal Scale (MNWS)** (77): The MNWS, a DSM IV-based instrument that assesses symptoms of nicotine withdrawal, will be used to track participants' nicotine withdrawal symptoms.
3. **Modified Cigarette Evaluation Questionnaire (mCEQ)** (78,79): The 12-item mCEQ assesses the reinforcing effects of smoking and contains 5 subscales (smoking satisfaction, psychological reward, enjoyment of respiratory tract sensations, craving relief, aversion).
4. **Craving and Temptation to Smoke:** These will be assessed on 10-point scales at every visit.

C3f. Statistical Methods

Outcome Measures

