The primary efficacy outcome is cotinine-verified 7-day point prevalence abstinence at the end of treatment (Week 12). The primary safety outcome is frequency of treatment-emergent adverse events.

Sample Size and Power

The proposed study is powered on the primary efficacy hypothesis that varenicline will increase abstinence (cotinine verified 7-day point prevalence abstinence), relative to placebo, at the end of treatment (Week 12). While 30-day point prevalence abstinence or continuous abstinence outcomes are ideal, we do not believe an adequately powered study for either approach is feasible within the proposed funding period. There is considerable precedent for using 7-day point prevalence as primary outcome in adolescent smoking cessation pharmacotherapy trials (see **Table 1**). We have recently published a conversion method to estimate continuous abstinence from point prevalence outcomes with a fair degree of confidence (80), and we will track other abstinence outcomes as secondary measures.

The first step towards a sample size analysis is estimating cotinine-confirmed 7-day point prevalence abstinence at end of placebo treatment. We estimate this to be 6.25%, based on the placebo-only end of treatment group abstinence rate in our prior bupropion SR/contingency management smoking cessation study, which was conducted in a nearly identical population to that of the proposed study (15). This estimate is consistent with placebo group end of treatment outcomes in other adolescent smoking cessation trials (e.g., 5% in Moolchan et al., 2005; 5.6% in Muramoto et al., 2007) (17,19). The slightly higher rate in our trial will result in a conservative estimate of the expected effect size (active – placebo), thereby increasing sample size and ensuring sufficient power for hypothesis testing.

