Categorical clinical and demographic variables will be assessed by chi-square tests of independence, while continuous variables will be assessed using Student's *t*-test. The effect of varenicline versus placebo on abstinence at end of treatment will be examined using logistic regression. Models will be computed both unadjusted and adjusted for significant covariates found in the descriptive analysis. For these efficacy analyses, 7-day point prevalence abstinence will be defined as having no cigarettes (or other tobacco/nicotine products) for 7 days, confirmed by urine cotinine level ≤ 50 ng/mL. All randomized participants will be included in the analyses (intent-to-treat approach), and participants will be considered non-abstinent at any missed visit.

Safety: Primary Analysis

Similar to adult varenicline phase III studies (23,24), we define any treatment-emergent adverse event any adverse event occurring between treatment initiation and one week following treatment conclusion. Non-inferiority analysis will be utilized to compare adverse event rates between varenicline and placebo groups (84). With a type 1 error rate of 5% ($\alpha = 0.05$) and power ($1 - \beta$) of 80%, the proposed total sample size of 166 and an estimated placebo rate of treatment-emergent adverse events of 75% (23) will afford a non-inferiority margin (NIM) of 16.7% for the varenicline adverse event rate. We considered incorporating a larger sample

Pro00014398

size that would afford a smaller NIM. However, even to detect a 12.5% NIM, a total sample size of 376 participants would be necessary. That sample size would not be feasible within the proposed funding period.

Smoking-Related Outcomes: Secondary Analysis

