Secondary outcomes include the following: a) 7-day biologically confirmed point prevalence abstinence at 6 months, b) continuous abstinence, c) time to lapse (first puff), d) time to relapse (first of 3 consecutive days smoking ≥ 1 cigarette), and e) longitudinal efficacy of varenicline. These will be tested via logistic regression to examine a) point prevalence at 6 months and b) continuous abstinence from targeted quit date (Week 1) to both treatment conclusion (Week 12) and final follow-up visit (Week 26), Cox Proportional hazard models (83) to examine c) time to first lapse (first puff, first cigarette), d) time to relapse (first of 3 consecutive days smoking ≥ 1 cigarette), and e) Generalized Estimating Equation (repeated measures) to examine the entire study time course. Repeated measures analysis of variance will be used to assess treatment effects of varenicline on craving (QSU-B), withdrawal (MNWS), and smoking reinforcement (mCEQ) throughout the study. All efficacy analyses (primary and secondary) will be repeated among participants with $\geq 80\%$ medication adherence, per protocol analysis, and completers analysis. Medication adherence (pill counts), nicotine dependence (mFTQ, AUTOS), motivation/readiness to quit (baseline rating), self-efficacy (GSES), perceived social support (MSPSS), and impulsivity (BIS-11) will be explored as possible moderators influencing the effect of varenicline on abstinence.

Safety: Secondary Analysis

Of particular interest will be adverse events leading to medication discontinuation and the occurrence of treatment-related serious adverse events (SAEs) (see Human Subjects Section 4.6). We will specifically compare neuropsychiatric adverse events (Psychiatric Interview) using non-inferiority testing, as well as depression/anxiety (HADS) and suicidality (C-SSRS) ratings using one-sided 2-sample t-tests. Based on adult literature (34,35), we anticipate no serious adverse events, and appropriate stopping plans are in place (see section C3g) for added precaution.

Participant Retention Analysis

Total number of treatment visits attended will be compared using a Student's *t*-test, while the number of days retained will be assessed using Cox Proportional Hazards regression models.

C3g. Clinical Management Issues

Study Termination

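### The only serious adverse event outcome named in the secondary safety analysis is limited to treatment-related events, with no cut-off for related and no all-cause summary by arm

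*Combined protocol and SAP*

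**What the plan says.** Section C3f, Safety: Secondary Analysis, opens: "Of particular interest will be adverse events leading to medication discontinuation and the occurrence of treatment-related serious adverse events (SAEs". It names no test, estimate or analysis set for SAEs, and it mentions no summary of SAEs regardless of cause.

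Relatedness is defined in Section C3e, Medication Monitoring and Safety/Tolerability Assessments, item 5: "The study medical clinician will additionally assess relatedness of adverse events to study interventions (i.e., not at all, unlikely, uncertain, possible, probable, definite". Neither C3e nor C3f says which of the six levels count as treatment-related. The rating is made under blinding; Section C3c says of eligible volunteers that "they will be randomized to double blind varenicline or placebo".

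The primary safety analysis is different in kind. Under Outcome Measures, "The primary safety outcome is frequency of treatment-emergent adverse events". Safety: Primary Analysis defines such an event as "any adverse event occurring between treatment initiation and one week following treatment conclusion", and adds: "Non-inferiority analysis will be utilized to compare adverse event rates between varenicline and placebo groups". No relatedness filter applies there. Nor does one apply to the neuropsychiatric adverse event, HADS and C-SSRS comparisons in the secondary analysis, or to events leading to discontinuation.

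Human Subjects Section 4.6 defines an SAE without regard to cause, and Section 4.9 requires SAEs of any cause to be reported within 24 hours.

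**The concern.** In a randomised placebo-controlled trial, the count of all SAEs by arm needs no causal judgement about individual events, because randomisation supplies the comparison. A count restricted to related events adds a subjective step after randomisation. That has two consequences here.

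First, the count is not reproducible from the plan. With six levels and no cut-off, two analysts could report different numbers of treatment-related SAEs from the same data, and the cut-off could be settled after unblinding.

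Second, events can drop out. The plan expects no SAEs at all, so any that occur will be few and each one matters. Psychiatric events in adolescents, the subject of the boxed warning that the protocol discusses at length, may be hard to attribute to drug or to background. A final report that followed C3f literally could state that there were no treatment-related SAEs and say nothing about the arms in which the other SAEs fell.

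**Working it through.** **1. The plan's own safety figure.** The SAE sentence has no number to reproduce. The nearest is the 16.7% non-inferiority margin in Safety: Primary Analysis. Inputs from that paragraph: total 166 (83 per arm), placebo rate 75%, power 80%, type 1 error 5%, taken here as one-sided.

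Margin = (z₀.₉₅ + z₀.₈₀) × √(2 × 0.75 × 0.25 / 83) = 2.486 × √0.004518 = 2.486 × 0.0672 = 0.167.

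The figure reproduces. It rests on adverse events of any cause, so the relatedness filter does not affect it.

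**2. Does the primary contrast cover SAEs?** It counts an SAE inside the window, but cannot show it separately. At a 75% rate, 0.75 × 83 = 62.25 placebo participants are expected to have some adverse event, and a participant with any mild event is already counted. The margin corresponds to 0.167 × 83 = 13.9 participants. A split of 6 SAEs to 0 is 6/83 = 7.2 percentage points, under half the margin, even if none of those six participants had any other event.

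**3. The window.** Treatment ends at Week 12, so the treatment-emergent window closes at Week 13. The last visit is Week 26. SAEs in the 13 weeks between are outside the primary contrast.

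**4. The remaining comparisons, side by side.**

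| Analysis in C3f | Relatedness filter? | Isolates serious events? |
|---|---|---|
| Treatment-emergent adverse events (primary) | No | No |
| Neuropsychiatric adverse events | No | No; psychiatric events only |
| HADS and C-SSRS ratings | No | No; rating scores |
| Adverse events leading to discontinuation | No | No |
| SAEs | **Yes, cut-off undefined** | Yes |

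The only line that isolates serious events is the one with the filter.

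**5. How much could the filter remove?** The documents give neither an SAE rate nor an attribution rate, so both are assumed here. For true SAE risk p in an arm of 83 and a share a rated related, expected related events = 83 × p × a, and the chance of seeing none = (1 − p × a)^83.

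| Assumed p | Share rated related, a | Expected count | Chance of zero |
|---|---|---|---|
| 6% | all SAEs | 5.0 | 0.6% |
| 6% | 80% | 4.0 | 1.7% |
| 6% | 50% | 2.5 | 8.0% |
| 6% | 20% | 1.0 | 37% |
| 2% | all SAEs | 1.7 | 19% |
| 2% | 20% | 0.3 | 72% |

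With equal attribution in both arms, 5.0 versus 1.7 expected events become 1.0 versus 0.3. The ratio stays near 3 to 1, but the absolute difference falls from about 3.3 events to 0.7.

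**6. What any SAE summary can show at this size.** With 83 per arm, zero events in an arm leaves a one-sided 95% upper bound of 1 − 0.05^(1/83) = 3.5%; one event gives 5.6% and two give 7.4%. Fisher's exact test, two-sided, gives p = 0.059 for 5 versus 0 and p = 0.028 for 6 versus 0. With assumed rates of 1% and 5%, power is about 12%. The summary is descriptive with or without the filter.

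**The case against.** The case on the other side is substantial. The sentence expresses emphasis; it does not say other SAEs will be left out, and the between-arm comparisons that the paragraph does specify do not include SAEs. The primary safety contrast is free of any relatedness filter, and an SAE in its window counts whatever its cause. The boxed-warning concern is addressed in the same paragraph through unfiltered neuropsychiatric comparisons. SAEs of any cause are defined, collected and reported, and item 5 of C3e has the monitoring board evaluate adverse event information by treatment group. All of that stands. It limits the point, but it does not supply a final summary of all SAEs by arm: monitoring is not the final analysis, and the unfiltered analyses do not separate serious events.

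Three stronger readings are tempting, and the documents do not support them.

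- A reader might infer that the trial's key safety contrast rests on clinician attribution. It does not: that contrast is treatment-emergent events of any cause by arm.
- A reader might infer that the SAE result will be biased, because recognisable side effects let the clinician suspect allocation. Item 7 of C3e does provide that "The study clinician will also document whether they think the participant is receiving active medication or placebo", but this checks the blind and does not show that it fails. One can assume a 4% SAE rate in both arms (3.3 events each) with 60% rated related on varenicline and 20% on placebo, and obtain 2.0 versus 0.7 events. That apparent threefold excess comes entirely from the assumed split, for which the documents give no basis.
- A reader might infer that SAEs rated uncertain necessarily drop out, since that level is listed before possible and Section 4.9 refers to events at least possibly related. That wording is a reporting threshold. No analysis cut-off is set, so where such events fall is open.

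**Conclusion.** The point holds as a gap in a secondary, descriptive outcome. C3f names only treatment-related SAEs, the deciding rating is subjective, its cut-off is undefined, and no other analysis in the plan isolates serious events or commits to an all-cause SAE summary by randomised arm.

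The consequence that can be supported is loss of information, together with a count that cannot be reproduced from the plan. On the assumptions shown (6% SAE risk, 83 in the arm), the chance of reporting zero in that arm moves from 0.6% to between 1.7% and 37% as the share rated related falls from 80% to 20%. These rates are illustrative; the plan itself anticipates no SAEs. The size and direction of any attribution bias cannot be determined from the documents. The 16.7% margin, the sample size and the primary analyses are unaffected.

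**What to change.** Amend Section C3f, Safety: Secondary Analysis, along these lines:

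*All serious adverse events, and all psychiatric serious adverse events, will be summarised by randomised arm regardless of judged relatedness, as counts and proportions of participants with exact 95% confidence intervals. Relatedness will be shown as a supplementary column at every level of the six-level scale.*

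Showing every level removes the need to choose a cut-off; whether uncertain is grouped with the related levels is then a matter of preference. It would also help to state that the summary runs to the Week 26 visit and to mark events after the treatment-emergent window.

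The cost is a wording change. It needs no new data, since Section 4.9 already covers SAEs of any cause, and no change to the sample size or any stated figure. The only downside is a few unrelated events in the table.

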The second was our recently completed pilot cessation trial, detailed below (Section C1b) (27). Briefly, we demonstrated 1) varenicline may produce abstinence rates superior to other medications, 2) no serious adverse events or discontinuation due to adverse events with varenicline, and 3) feasibility of conducting varenicline smoking cessation trials in adolescents.

The proposed study will have numerous clinical and policy implications. First, there are few options for smoking cessation among adolescent smokers, despite clear evidence that the trajectory of smoking is most malleable during this formative period (28,29). The existing treatment options produce modest effects at best. Many physicians are willing to prescribe a medication off-label to adolescents, particularly if that medication has a strong base of support within another population (30,31). We believe many physicians are either already using varenicline in adolescents on their own accord, or wish to do so. This study will provide the necessary data to support or refute this strategy. Second, we recognize that use of varenicline includes potential added risk, given recent anecdotal reports of psychiatric instability (32,33). Despite the FDA's strong reaction to those anecdotal reports, the vast majority of scientific evidence supports the safety of varenicline. This includes a pooled analysis of 3091 participants randomized to varenicline in controlled trials, revealing no significant increase (relative to placebo) in psychiatric symptoms, aside from sleep disturbance (34) (**Table 2**). Additionally, a "real world" primary care cohort study including 10,973 smokers prescribed varenicline revealed no evidence of increased risk of self-harm, compared with smokers prescribed other cessation pharmacotherapies (35). Nonetheless, the FDA regulatory constraint, including a "black box" warning, remains. We do not suggest that our study alone will provide the necessary information for a change in FDA regulatory practice, nor will our study provide sufficient support for a change in indication for varenicline. It will, however, provide valuable evidence regarding varenicline's potential viability as a treatment for adolescent smokers.

Table 2. Adverse events (AEs) in pooled analysis of varenicline controlled trials (34)

	Varenicline ($n = 3091$)	Placebo ($n = 2005$)	RR	95% CI	
Any Psychiatric AE (excluding sleep disturbances)	10.7%	9.7%	1.02	0.86-1.22	

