14. **Multidimensional Scale of Perceived Social Support (MSPSS)** (67, 68): The MSPSS is an adolescent-validated 12-item instrument that assesses perceived support from family, friends, and a significant other.
15. **Barratt Impulsiveness Scale (BIS-11)** (69): The BIS-11 is an adolescent-validated 30-item self-report questionnaire of impulsive personality traits.
16. **Toronto Alexithymia Scale (TAS-20)** (87): The TAS is a scale which measures alexithymia, a condition in which people have trouble identifying and describing feelings. Items are rated using a 5-point Likert scale whereby 1 = strongly disagree and 5 = strongly agree. Both the original, 1985 version and the revised, 1992 version will be administered at the assessment visit.
17. **Wisconsin Predicting Patient's Relapse (WI-PREPARE)** (88): The WI-PREPARE is a 7-item scale that predicts relapse to smoking through assessment of nicotine physical dependence, environmental factors, and individual difference characteristics.
18. **Technology Acceptability Questionnaire**: This 54-item, locally developed questionnaire will be administered to participants once during the course of the study to gain information on their technology use and acceptability.

Psychiatric Symptom Assessments (to be administered at all visits)

1. **Psychiatric Interview**: The study medical clinician (directly supervised by the PI, a board certified child & adolescent psychiatrist) will conduct an interview inquiring about symptoms of depression, mania/hypomania, pathological anxiety, psychosis, substance abuse, sleep disturbance, and suicidality since the last visit. The screening items from the MINI (56,57) will be modified for use as a prompt to evaluate all major components of psychiatric symptomatology.
2. **ADHD Rating Scale-IV (ADHD-RS)** (70): This validated measure will assess ADHD symptom severity.
3. **Hospital Anxiety and Depression Scale (HADS)** (71-73): This self-report instrument, validated in adolescents and adults, will be used to monitor anxiety and depression symptoms.

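### The non-inferiority test of neuropsychiatric adverse events has no margin, alpha or event definition, and the plan's only adopted margin was sized for a much commoner endpoint

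*Combined protocol and SAP*

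**What the plan says.** The secondary safety paragraph of section C3f states: "We will specifically compare neuropsychiatric adverse events (Psychiatric Interview) using non-inferiority testing". The same sentence assigns the depression/anxiety scale (HADS) and "suicidality (C-SSRS) ratings using one-sided 2-sample t-tests". It gives no margin, alpha, expected rate or power for the neuropsychiatric comparison. It also does not say which interview findings count as events, or whether the unit is the participant or the event. For the two scales it names no visit, no score (raw or change) and no baseline adjustment.

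The only margin the plan adopts is in the primary safety paragraph. With alpha 5%, power 80% and a 75% placebo rate of any treatment-emergent event, a total of 166 "will afford a non-inferiority margin (NIM) of 16.7% for the varenicline adverse event rate". A tighter margin is mentioned there and set aside as infeasible: "even to detect a 12.5% NIM, a total sample size of 376 participants would be necessary".

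Three other places bear on the point:

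- Table 2 in section A (adult pooled data) gives any psychiatric event, excluding sleep disturbances, as 9.7% on placebo and 10.7% on varenicline. It gives sleep disturbances separately as 14.5% and 25.1%.
- Section C3e lists sleep disturbance among the symptoms the Psychiatric Interview asks about. It schedules the interview, the HADS and the C-SSRS at every visit.
- Section C3b excludes anyone with a lifetime mood or psychotic disorder or lifetime suicidality.

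**The concern.** A non-inferiority conclusion is only as strong as its margin. If none is set beforehand, it can be chosen once the data are known, and that choice decides the verdict. The natural candidate is the one margin in the document. But 16.7 points was worked back from the sample size for an endpoint expected in three participants out of four. On an endpoint expected in about one in ten, the same number of points is a very large relative increase: 9.7% + 16.7 = 26.4%, which is 2.7 times the placebo rate.

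Psychiatric harm is the subject of the boxed warning that the protocol discusses at length, and section A says the results will inform prescribing to adolescents. A statement that varenicline was non-inferior for neuropsychiatric events would be quoted, so a reader must be able to see what it excludes.

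The two rating scales raise a related problem. Both are measured at every visit, yet the analysis is a two-sample t-test whose input is not identified.

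**Working it through.** **Inputs.** 83 per arm, power 80% and a 75% any-event placebo rate (section C3f); 9.7% placebo rate for psychiatric events without sleep disturbances, and 14.5% for sleep disturbances (Table 2, section A).

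**1. Reproduce the plan's margin.** With equal true rates p, margin = (z(1−α) + z(0.80)) × √(2p(1−p)/83).

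- One-sided 5%: (1.645 + 0.842) × √(2 × 0.75 × 0.25/83) = 0.167. This matches the plan.
- One-sided 2.5%: 0.188. This does not match.

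The other figure in that paragraph points the other way. The total for a 12.5-point margin is 4 × 0.75 × 0.25 × (z(1−α) + z(0.80))²/0.125². That is 296.8 at one-sided 5% and 376.7 at one-sided 2.5%; the plan says 376. The two figures rest on different alphas, so the paragraph does not settle the sidedness, and both are carried below.

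**2. Margin afforded at 9.7%.** (1.645 + 0.842) × √(2 × 0.097 × 0.903/83) = 0.114, or 11.4 points. A doubling is a difference of 9.7 points, so even a margin sized for this endpoint at this N would accept one. A 9.7-point margin would have 68% power with 83 per arm (equal rates, one-sided 5%) and would need 116 per arm for 80%.

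**3. Carry the 16.7-point margin over.** Non-inferiority is declared when the upper Wald limit of the risk difference is below 0.167. For a doubling from 9.7% to 19.4%:

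- SE = √((0.097 × 0.903 + 0.194 × 0.806)/83) = 0.0542.
- One-sided 5%: Φ((0.167 − 0.097)/0.0542 − 1.645) = 36%. Exact binomial enumeration gives 37%.
- One-sided 2.5%: 25% by the approximation, 27% by enumeration.

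For example, an observed 8/83 against 14/83 (75% more events) has an upper one-sided 95% limit of 15.8 points and would pass. At one-sided 2.5% the most that would pass against 8/83 is 13/83.

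**4. Vary the placebo rate.** The trial's own rate is unknown. The 5% row is an assumption, to allow for the exclusion of people with a psychiatric history. If sleep disturbance counts, the adult composite lies between 14.5% (full overlap with other psychiatric events) and 9.7 + 14.5 = 24.2% (no overlap). Probability that a true doubling is called non-inferior, exact enumeration, margin 16.7 points:

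| Placebo rate | Doubled rate | One-sided 5% | One-sided 2.5% |
|---|---|---|---|
| 5% | 10% | 88% | 81% |
| 9.7% | 19.4% | 37% | 27% |
| 14.5% | 29% | 10% | 5.5% |
| 24.2% | 48.4% | 0.3% | 0.1% |

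The pattern follows from the arithmetic: once the placebo rate exceeds 16.7%, a doubling lies outside the margin.

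**5. The scales.** The HADS and C-SSRS are collected at every visit, but the text does not say which value enters the t-test. The same section uses repeated-measures analysis for craving, withdrawal and smoking reinforcement. For the C-SSRS, lifetime suicidality is an exclusion and the pilot (29 participants) recorded no suicidal ideation or behavior, so mostly zero scores are likely, and a comparison of means suits such data poorly.

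**The case against.** The strongest reply is that the 16.7-point margin is borrowed. The plan ties it to the overall adverse event rate and nowhere applies it to neuropsychiatric events. A reader might infer that the plan would pass a doubling of psychiatric events more than a third of the time. The documents do not support that as a property of the plan: it needs the borrowed margin, one-sided 5%, and an adult rate that leaves out a symptom the Psychiatric Interview covers. If sleep disturbance is counted, the figure is 10% or lower. This objection stands, and the calculation is offered only as what would follow if the margin were carried over. It does not remove the gap, because if 16.7 points does not apply then no margin exists. A result running from 0.3% to 88% with event definition and placebo rate is itself a reason to fix both beforehand.

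A reader might also infer that the t-tests ignore baseline. The text does not go that far: it names no score, so change from baseline is not ruled out. What can be said is that the input is unspecified. Nor do the documents give a C-SSRS distribution; mostly zero scores are an expectation.

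It is also fair to say that this is a secondary analysis, that participants are protected by weekly clinical review and quarterly board review, and that an upper confidence limit carries the same information as a non-inferiority test. The first two limit the consequence without repairing the inference. The third favors reporting the limit itself, which needs no margin.

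**Conclusion.** The point holds as a gap in specification. The neuropsychiatric non-inferiority test has no margin, alpha or event definition, and the only adopted margin comes from a 75% event rate and is not said to apply. Carried over, it would call a true doubling non-inferior 37% of the time (27% at one-sided 2.5%) at a 9.7% placebo rate, with a range at one-sided 5% from 88% at 5% to 0.3% at 24.2%. These figures assume 83 evaluable participants per arm and a Wald limit; the placebo rates are adult figures or assumptions. Supplying a margin would not rescue the test, because at 9.7% this sample size affords 11.4 points, still more than a doubling. The HADS and C-SSRS analyses are under-specified, and the t-test is a poor choice for the C-SSRS. The change should be made, but it concerns a secondary endpoint and does not touch the primary efficacy analysis.

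**What to change.** In the secondary safety paragraph of section C3f, before unblinding:

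- Replace the neuropsychiatric non-inferiority test with the number and percentage of participants with at least one event per arm, and the risk difference with a two-sided 95% confidence interval. Define which interview findings count, and report the result with and without sleep disturbances. Limit the conclusion to the size of increase that the upper limit excludes.
- Analyze the HADS with a baseline-adjusted repeated-measures model over the scheduled visits, reporting the treatment difference with a two-sided interval.
- Analyze the C-SSRS as any positive response during treatment, by arm, with an exact interval. Even no positive response among 83 would leave a two-sided 95% upper limit of 1 − 0.025^(1/83) = 4.3%, which is worth stating.

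The cost is SAP wording only; no new data, visits or participants are needed. The sponsor gives up a statement of non-inferiority on this secondary endpoint.
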